11.4 Second Malignancies

Patients will be followed for the development of second cancers, including lymphoproliferative disorder and myelodysplasia/myeloproliferative disorder. See Section 7.3.2

11.5 Evaluation of Response

All participants included in the study must be assessed for response to treatment, even if there are major protocol treatment deviations or if they are ineligible. Each participant should be assigned one of the following categories: 1) complete remission, 2) complete remission without neutrophil or platelet recovery, 3) persistent disease, 4) early death from leukemia 5) early death from toxicity, or 6) unknown (not assessable, insufficient data). World Health Organization (WHO) criteria will be used to assess response. Patients will be assessed for complete remission or complete remission without platelet recovery per WHO criteria. (43) Patients who experience toxicity but die with persistent leukemia will be classified as 3) death of persistent disease.

Morphologic Complete Remission (CR):

Defined as morphologic leukemia-free state, including <5% blasts in Bone Marrow aspirate with marrow spicules, no persistent extramedullary disease, ANC >1000/mm³ and platelet count >100,000/mm³.

Morphologic Complete Remission without neutrophil (CRi) or platelet recovery (CRp):

Defined as CR with the exception of neutrophil count < 1,000/mm³ (CRi) or platelet count < 100,000/mm³ (CRp).

Persistent Disease:

Greater than 5% blasts in the marrow.

CONFIDENTIAL

This document is confidential. Do not disclose or use except as authorized.

Recurrence/morphologic relapse:

Defined as reappearance of >5% blasts in the bone marrow, not attributable to any other cause, *after* the documentation of complete remission (CR)

Early death from leukemia:

Defined as death within 50 days of treatment attributed to persistent leukemia.

Early death from toxicity:

Defined as death within 50 days of start of treatment attributed to therapy in the absence of leukemia.

11.6 Transfusion Requirements

Patients will receive transfusion support per institutional guidelines. The number of red blood cell and platelet transfusions needed in the first 50 days of treatment will be assessed.

12. DATA REPORTING / REGULATORY REQUIREMENTS

Adverse event lists, guidelines, and instructions for AE reporting can be found in Section 7.0 (Adverse Events: List and Reporting Requirements).

12.1 Data Reporting

12.1.1 Method

The Office of Data Quality (ODQ) will collect, manage, and perform quality checks on the data for this study.

12.1.2 Responsibility for Data Submission

Participating sites within are responsible for submitting data and/or data forms to the ODQ according to the schedule set by ODQ.

12.2 Data Safety Monitoring

The DF/HCC Data and Safety Monitoring Committee (DSMC) will review and monitor toxicity and accrual data from this study. The committee is composed of clinical specialists with experience in oncology and who have no direct relationship with the study. Information that raises any questions about participant safety will be addressed with the Overall PI and study team.

The DSMC will review each protocol up to four times a year or more often if required to review toxicity and accrual data. Information to be provided to the committee may include: up-to-date participant accrual; all grade 2 or higher unexpected adverse events that have been reported; summary of all deaths occurring with 30 days of intervention for Phase I or II protocols; any

CONFIDENTIAL

This document is confidential. Do not disclose or use except as authorized.

response information; audit results, and a summary provided by the study team. Other information (e.g. scans, laboratory values) will be provided upon request.

12.3 Multicenter Guidelines

This protocol will adhere to the policies and requirements of the DF/HCC Multi-Center Data and Safety Monitoring Plan. The specific responsibilities of the Overall PI, Coordinating Center, and Participating Institutions and the procedures for auditing are presented in Appendix B.

- The Overall PI/Coordinating Center is responsible for distributing all IND Action Letters or Safety Reports to all participating institutions for submission to their individual IRBs for action as required.
- Mechanisms will be in place to ensure quality assurance, protocol compliance, and adverse event reporting at each site.
- Except in very unusual circumstances, each participating institution will order the study agent(s) directly from supplier. A participating site may order the agent(s) only after the initial IRB approval for the site has been forwarded to the Coordinating Center.

12.4 Collaborative Agreements Language

N/A

13. STATISTICAL CONSIDERATIONS

Primary objective

This is a single arm study to evaluate the efficacy of lenalidomide in combination with reinduction chemotherapy (mitoxantrone/etoposide/cytarabine) for patients with relapsed or refractory AML.

Sample size

The primary endpoint is complete remission (CR) and CRp after MEC+lenalidomide. A 45% complete remission rate will be considered clinically significant. The response evaluation will be assessed after the first (and only) cycle of treatment. There is no retreatment as a part of this protocol. We will plan to evaluate patients who receive the study treatment; we will plan to replace up to 2 patients who are not able to complete the ten days of therapy.

A two-stage design is considered here. A total number of 40 patients is needed in order to detect a 20% response rate increase, assuming the null hypothesis is 25%, with a 90% power and 9% one-sided type I error rate. The study will be reevaluated if 4 or fewer responses out of 18 patients are observed and the treatment will be declared inactive if fewer than 14 responses are seen in the total 40 patients. Factors during treatment, such as the rate of treatment completion, may be considered in evaluating any responses. The probability of stopping at the first stage is 0.52, if the true response rate is 25%.

We chose this study design over other possible phase II study designs, including randomized phase II designs, because it is powered toward identifying a clinically significant improvement in response (20% increase compared to historical rates); a smaller randomized study may be underpowered to identify the true response rate.

Primary analysis

The rate of CR+CRp will be calculated along with the corresponding 90% two-stage exact binomial CI.

The analyses for secondary objectives will be descriptive in nature. Proportion of patients with ANC recovery/platelet recovery (as defined in Section 11.1) will be reported, along with median days to counts recovery. Total transfusion requirements will be reported as the median and range of each blood product. Cumulative incidence of treatment related mortality (defined in Section 11.2) will be estimated using relapse and early death from relapse as competing risks. Overall survival and Relapse-free survival (defined in Section 11.3) will be estimated using the Kaplan-Meier method.

Participants who never start protocol therapy, or who do not complete the 10 days of protocol based chemotherapy will be excluded from the analyses and will be replaced. The estimated accrual period is 2.5 years.

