Simon's two stage optimal design is used to compute the sample size. A total number of 40 patients is needed in order to detect a 20% CR rate increase assuming the CR for null hypothesis is 25% with a 90% power and 9% type I error. The study will be reevaluated if 4 or fewer responses out of 18 patients are observed and the study will be declared inactive if fewer than 14 responses are seen in the total 40 patients. The probability of stopping at the first stage is 0.52.

Accrual Objective: 40 - 42 patients in order to enroll 40 evaluable patients.

Accrual Period: The estimated accrual period is 2.5 years

Eligibility Criteria:

The following criteria must be met prior to enrolling.

- Acute myelogenous leukemia diagnosed by WHO criteria with one of the following:
 - Primary refractory disease following ≥ 1 cycle of induction chemotherapy.

CONFIDENTIAL

This document is confidential. Do not disclose or use except as authorized.

- First relapse or higher. Patients with primary or secondary acute myelogenous leukemia are eligible. Patients with biphenotypic leukemia are eligible.
- 18-70 years
- LVEF \geq 50%
- ECOG Performance status 0-2
- Creatinine < 2.0 mg/dl and eGFR ≥ 60 mL/min.
- Total bilirubin $< 1.5 \times$ institutional ULN
- AST (SGOT) and ALT (SGPT) $\leq 3 \times$ institutional ULN
- Able to adhere to study schedule and other protocol requirements
- Patients may receive hydroxyurea, steroids, or leukapheresis as necessary until Day 5 of treatment.

Treatment Description:

Patients will receive only one cycle of treatment, as below:

1. Lenalidomide Days 1-10
2. Mitoxantrone by IV infusion over approximately 6-10 minutes for 5 days (days 4-8)
3. Etoposide IV over approximately 1 hour daily for 5 days (days 4-8)
4. Cytarabine IV over approximately 1 hour daily for 5 days (days 4-8).

	Day 1	Day 2	Day 3	Day 4	Day 5	Day 6	Day 7	Day 8	Day 9	Day 10
Mitoxantrone (intravenous)				X	X	X	X	X		
Etoposide (intravenous)				X	X	X	X	X		
Cytarabine (intravenous)				X	X	X	X	X		
Lenalidomide (oral)	X	X	X	X	X	X	X	X	X	X

Study Duration:

Participants will be followed for at least 50 days after the start of protocol treatment.

Participants will be followed for relapse and survival at 3 months after treatment, and then every six months until 3 years from start of treatment. Patients removed from the study treatment will continue to be followed for relapse and survival for up to three years following initiation of study treatment

CONFIDENTIAL

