6. DOSING DELAYS/DOSE MODIFICATIONS

Any dose modifications or delays in the reinduction chemotherapy regimen of mitoxantrone, etoposide, and cytarabine should be per the treating physician and institutional practice, with approval from the overall PI (also please refer to section 6.3, table 5).

There may be two dose reductions in lenalidomide per patient. Reduction of lenalidomide dose may be modified as follows:

Table 3: Lenalidomide Dose Reductions	
Dose Level	Lenalidomide dose
1 (starting dose)	50 mg
-1	25mg
-2	10 mg

No Lenalidomide will be given after Day 10, even if there are missed doses.

Dose delays and modifications will be made as indicated in Table 4. The descriptions and grading scales found in the revised NCI Common Terminology Criteria for Adverse Events (CTCAE) version 4.03 will be utilized for dose delays and dose modifications. A copy of the CTCAE version 4.03 can be downloaded from the CTEP website http://ctep.cancer.gov/protocolDevelopment/electronic_applications/ctc.htm.

CONFIDENTIAL

This document is confidential. Do not disclose or use except as authorized.

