11.2 Treatment-related Mortality

All deaths in the absence of relapse of the primary malignancy will be considered treatment

CONFIDENTIAL

This document is confidential. Do not disclose or use except as authorized.

related mortality. The cumulative incidence of treatment related mortality at 50 days will be measured.

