13.1.1 Evaluation of toxicity

All participants will be evaluable for toxicity from the time of their first treatment up until day 50 or the initiation of other therapy. In the phase I study of 35 patients, 3 dose limiting toxicities were noted due to prolonged count recovery. In the current study, we will monitor for toxicities and assess them as a part of the two stage design described above. If, within the first 10 patients on study, 3 or more experience prolonged neutrophil or platelet recovery beyond day 45 in the absence of disease, or other unacceptable toxicities felt related to the study regimen, we will put the study on hold to investigate further enrollment. The probability of putting the study on hold is 7%, if the true probability of delayed count recovery is 10%.

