13.1.2 Evaluation of the Primary Efficacy Endpoint

Analyses will be performed on an intent-to-treat basis. Specifically, all eligible participants, except those who are removed and replaced, who are then included in the study, will be assessed for response/outcome to therapy, even if there are major protocol therapy deviations.

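### The denominator of the primary CR+CRp rate is not fixed: one rule drops and replaces every treated non-completer, others cap replacement at two or require everyone to be assessed

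*Combined protocol and SAP*

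**What the plan says.** Five places bear on who enters the CR+CRp denominator.

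- **Section 13, paragraph before 13.1.1.** Patients who never start, and those "who do not complete the 10 days of protocol based chemotherapy will be excluded from the analyses and will be replaced". No maximum is given.
- **Section 13, Sample size.** The plan is to evaluate patients who receive study treatment, and "we will plan to replace up to 2 patients who are not able to complete the ten days of therapy".
- **Synopsis, Accrual Objective.** "40 - 42 patients in order to enroll 40 evaluable patients", which fits a cap of two.
- **Section 13.1.2.** The analysis is labelled intent-to-treat, but "all eligible participants, except those who are removed and replaced, who are then included in the study, will be assessed for response/outcome to therapy".
- **Section 11.5.** All included participants "must be assessed for response to treatment, even if there are major protocol treatment deviations or if they are ineligible". Early death from leukemia and early death from toxicity are listed as outcome categories.

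The decision rule in Section 13 is to re-evaluate the study at 4 or fewer responses in 18, and to declare the treatment inactive at fewer than 14 in 40. The null rate is 25% and the target 45%.

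**The concern.** Completing ten days is not a baseline characteristic. Section 5.5 ends therapy for progression or unacceptable adverse events, Section 6.2 stops lenalidomide for certain toxicities, and a death on Days 1-10 also prevents completion. Patients lost by death or progression are treatment failures. Removing them and enrolling others in their place raises the observed remission rate.

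Non-completers are not all failures, however. MEC ends on Day 8 and only lenalidomide runs to Day 10; Section 6 adds "No Lenalidomide will be given after Day 10, even if there are missed doses". A patient can receive all the MEC, miss lenalidomide doses and still remit. The text does not say whether that patient completed the ten days, and excluding a remitter would bias the rate downward.

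Because the rule is a hard cut-off, the same patients can produce opposite conclusions depending on which paragraph is followed. Section 13 also allows the treatment completion rate to be considered when responses are evaluated, which leaves room for judgment after outcomes are known.

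A smaller point concerns treatment-related mortality. The exclusion applies to the analyses in general, so it is unclear whether Day 1-10 deaths count. Section 11.2 ("All deaths in the absence of relapse of the primary malignancy") and Section 13.1.1 ("All participants will be evaluable for toxicity from the time of their first treatment up until day 50") point to counting them. This needs reconciling, but no bias is shown.

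**Working it through.** **1. The stated design.** Inputs from Section 13: n1 = 18, continue if more than 4 responses; N = 40, active if at least 14; p0 = 0.25, p1 = 0.45. With the first-stage stop treated as binding,

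P(active | p) = Σ over x = 5 to 18 of Bin(x; 18, p) × P(Bin(22, p) ≥ 14 − x).

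- P(active | 0.25) = 0.0949 (stated 9%)
- P(active | 0.45) = 0.9042 (stated 90%)
- P(Bin(18, 0.25) ≤ 4) = 0.5187 (stated 0.52)

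The design reproduces. The open question is which patients make up the 18 and the 40.

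**2. Model for exclusion.** The documents give no non-completion rate, so d = 5%, 10% and 15% are assumed. Let non-completers remit at k times the completers' rate, and hold the all-treated rate at 25%. The completers' rate is then

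pc = 0.25 / [(1 − d) + d·k].

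For k = 0 this gives 0.263, 0.278 and 0.294.

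*Capped rule:* the first two non-completers are dropped and replaced, and later ones are counted at rate k·pc (exact recursion over patients). *Uncapped rule:* all are replaced, so P(active) is evaluated at pc.

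| Type I error | d = 5% | d = 10% | d = 15% |
|---|---|---|---|
| Cap of 2, k = 0 | 0.121 | 0.132 | 0.135 |
| Cap of 2, k = 0.5 | 0.107 | 0.111 | 0.112 |
| No cap, k = 0 | 0.132 | 0.183 | 0.250 |
| No cap, k = 0.5 | 0.112 | 0.132 | 0.156 |
| Either rule, k = 1 | 0.095 | 0.095 | 0.095 |

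At the boundary with two exclusions of non-remitters, 14/42 = 33.3% would be reported as 14/40 = 35.0%.

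**3. When the two replacement rules part.** They differ from the third non-completer onward. Among 42 treated patients, P(Bin(42, d) ≥ 3) = 0.351, 0.805 and 0.962.

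**4. A decision that flips.** Take 13 remissions in the first 40 treated, two of whom neither completed nor remitted, with the first stage passed. Counting all treated gives 13/40, inactive. Replacing the two (assuming both replacements complete) gives 14/40 or more if at least one replacement remits: 1 − 0.75² = 0.4375 at a 25% rate, 1 − 0.55² = 0.6975 at 45%.

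**5. Power if all treated patients are counted.** If 25% and 45% are all-treated rates, step 1 stands unchanged. If 45% was meant for completers, the all-treated rate is 0.45 × [(1 − d) + d·k]. Power is then 0.850, 0.778 and 0.687 for k = 0, and 0.880, 0.850 and 0.817 for k = 0.5.

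**The case against.** The strongest reply is that the Synopsis, the Sample size paragraph and Section 13.1.2 form one coherent rule: 40 evaluable patients with at most two replacements. Section 13.1.2 expressly excepts replaced patients, and Section 11.5 governs assigning a response category, not the denominator. Much of this is fair. The conflict with Section 13.1.2 is mainly with its intent-to-treat label, and Section 11.5 does not literally define the analysis set. It remains that the exclusion sentence has no cap, that nothing settles a third non-completer, and that Sections 11.5 and 13.1.2 disagree on ineligible patients.

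On size, no remission among non-completers is the worst case, and 0.250 further requires the uncapped sentence to override the cap and the 42-patient plan at 15% non-completion. With the cap and 2% non-completion, type I error is only 0.101 (k = 0.5) to 0.108 (k = 0). If 25% and 45% were meant as rates among evaluable patients, the stated error rates hold for that set; the documents do not say. These limits stand.

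The divergence probabilities assume 42 patients are treated. With a binding first-stage stop at a 25% rate and k = 0 they fall to about 22%, 61% and 83%. At a 45% rate the stop hardly matters (34%, 80%, 96%), and the text says only that the study will be re-evaluated. The flip example shows that a reversal is possible, not that it is likely: exactly 13 of 40 has a probability of about 8% at a 25% rate and 4% at 45%.

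**Conclusion.** The concern holds and must be fixed before the primary analysis. The plan has no single denominator for its primary endpoint, and the exclusion it describes depends on what happens after treatment starts. The sample size arithmetic itself is sound.

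The inflation of type I error is moderate under the capped reading and can be large under the uncapped one. It vanishes if non-completers remit as often as completers. All these figures rest on assumed non-completion rates and on 25% being an all-treated rate, which the documents do not allow to be checked. The contradiction between the paragraphs depends on none of these assumptions.

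**What to change.** - Define the primary set as all patients who receive at least one dose of protocol therapy, including any later found ineligible, in line with Section 11.5.
- Count documented CR or CRp as response whether or not ten days were completed. Count everyone else (early death, discontinuation or not assessable, without CR or CRp) as a non-responder.
- Replace only patients who never start; Section 4 already cancels those registrations.
- Keep 40 treated patients and the 4/18 and 14/40 rules. Use the same set for treatment-related mortality.
- Define what completing ten days means, and report completers as a sensitivity analysis.
- State whether 25% and 45% are all-treated or completer rates.
- Bring the Synopsis and Sections 11.5, 13 and 13.1.2 into agreement.

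The cost is a wording change and up to two fewer patients. The observed rate may be slightly lower. If the 45% target was meant for completers, power falls as shown in step 5 of the working, and the sponsor should then decide openly whether to accept that.

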13.1.1 Evaluation of toxicity

All participants will be evaluable for toxicity from the time of their first treatment up until day 50 or the initiation of other therapy. In the phase I study of 35 patients, 3 dose limiting toxicities were noted due to prolonged count recovery. In the current study, we will monitor for toxicities and assess them as a part of the two stage design described above. If, within the first 10 patients on study, 3 or more experience prolonged neutrophil or platelet recovery beyond day 45 in the absence of disease, or other unacceptable toxicities felt related to the study regimen, we will put the study on hold to investigate further enrollment. The probability of putting the study on hold is 7%, if the true probability of delayed count recovery is 10%.

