Protocol 12-202, Phase I study of Lenalidomide plus mitoxantrone, etoposide, and cytarabine for patients with relapsed and refractory AML has just been completed at DF/HCC. Results were presented in abstract form at the American Society of Hematology, December 2015. (54)

The primary objective of this Phase I trial was to evaluate the safety of lenalidomide in combination with MEC for relapsed acute myelogenous leukemia and determine a safe Phase II dose and schedule. The secondary objectives included time to neutrophil (>500) and platelet recovery ($> 20K$), the complete response rate with and without platelet recovery, and the treatment-related mortality within the first 45 days. Patients received lenalidomide in escalating doses at dose levels: 5 mg, 10 mg, 25 mg and 50 mg. Lenalidomide was given initially Days 1-14, and then due to neutropenia was decreased to Days 1-10. The chemotherapy was given as follows: Mitoxantrone $8 \text{ mg/m}^2/\text{day}$ Days 4-8, Etoposide $100 \text{ mg/m}^2/\text{day}$ Days 4-8, and Cytarabine $1000 \text{ mg/m}^2/\text{day}$ Days 4-8. Thirty-six patients were enrolled with a median age of 61 years. Forty-five percent of patients had received 2 or more prior chemotherapy regimens, and 22% had received a prior stem cell transplant. Thirteen patients entered complete remission and one patient had complete remission with incomplete count recovery for a response rate of 39%. The median time to ANC > 500 was 30 days and the median time to platelet recovery $> 20,000$ was 34 days. Two of 6 patients treated with lenalidomide for 14 days had no count recovery at Day 42. After the dose adjust to 10 days, only 1 of 13 patients at lenalidomide 50 mg daily x 10 days had prolonged count recovery. Thus, the recommended phase 2 dose is 50 mg daily for 10 days. There were 4 deaths on study, deemed unrelated to study drug. One patient died of sepsis, one of infection, and two of respiratory failure.

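### Toxicity is referred to a two-stage design that has response cut-offs only, so after patient 10 there is no pre-specified numeric toxicity trigger

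*Combined protocol and SAP*

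**What the plan says.** Section 13.1.1 states that "we will monitor for toxicities and assess them as a part of the two stage design described above". It then gives one numeric rule. The trigger is worded "If, within the first 10 patients on study, 3 or more experience prolonged neutrophil or platelet recovery beyond day 45", and it applies only to patients without disease. A second kind of event also counts, worded "or other unacceptable toxicities felt related to the study regimen". When the trigger is met, the study goes on hold while further enrolment is considered. One operating characteristic is given: "The probability of putting the study on hold is 7%, if the true probability of delayed count recovery is 10" per cent.

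The two-stage design is set out in the synopsis and section 13. At stage 1, "The study will be reevaluated if 4 or fewer responses out of 18 patients are observed". At the end, "the treatment will be declared inactive if fewer than 14 responses are seen in the total 40 patients". Section 13 adds that factors such as the rate of treatment completion may be considered when responses are evaluated. Neither place gives a toxicity limit.

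Section 12.2 has the DSMC review toxicity and accrual up to four times a year, or more often if required, with no threshold. Appendix B, section 3.2 provides for temporary holds with immediate effect.

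Section 2.4.1 gives the phase I background. "Two of 6 patients treated with lenalidomide for 14 days had no count recovery at Day 42", and lenalidomide was shortened to 10 days because of neutropenia. On 50 mg for 10 days, the schedule carried into this trial, 1 of 13 patients had prolonged count recovery.

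**The concern.** The cross-reference points to a toxicity criterion that does not exist. Once the tenth patient has been assessed, the only numeric rule has been used up, and 30 of the planned 40 patients (30 to 32 under the accrual objective of 40 to 42) follow. If 2 of the first 10 had prolonged aplasia and many later patients did too, no stated rule would pause the trial.

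Prolonged count recovery is the toxicity that section 13.1.1 names as dose-limiting in phase I. A single look at 10 patients has limited power to detect an excess, and the plan never says how limited, because it reports the hold probability only at a rate it regards as acceptable. The stage 1 look cannot be relied on to catch the problem, since it acts only when responses are few.

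**Working it through.** **Inputs.** Hold at 3 or more of 10; stated hold probability 7% at a 10% rate (13.1.1). Stage 1 cut-off of 4 or fewer responses of 18, stopping probability 0.52 at a 25% response rate, total 40 patients (13). Phase I rates 2/6 and 1/13 (2.4.1).

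**Step 1: reproduce the plan's figures.** With X ~ Binomial(10, p), P(hold) = P(X ≥ 3).
- At p = 0.10: 1 − (0.3487 + 0.3874 + 0.1937) = 0.0702, against the stated 7%.
- Stage 1: P(Binomial(18, 0.25) ≤ 4) = 0.5187, against the stated 0.52. This uses responses alone, which confirms that no toxicity criterion enters the design.

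**Step 2: the same rule at other rates.** P(X ≥ 3) is 0.322 at 20%, 0.474 at 25%, 0.617 at 30% and 0.701 at one third. The chances of no hold are 68%, 53%, 38% and 30%.

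**Step 3: can the stage 1 look substitute?** If the true response rate is 45%, P(Binomial(18, 0.45) ≤ 4) = 0.041. An effective regimen would pass that look about 96% of the time, and no toxicity count enters the decision.

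**Step 4: patients affected.** 40 − 10 = 30. Expected further events among 30 patients: 3 at 10%, 6 at 20%, 10 at one third.

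**Step 5: what a continued rule would do.** Take the 10-patient rule and add a cumulative hold at 5 or more of 18. With Y ~ Binomial(8, p),

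P(hold by 18) = P(X ≥ 3) + Σ (k = 0 to 2) P(X = k) · P(Y ≥ 5 − k).

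At p = 0.20: 0.3222 + 0.1074 × 0.0104 + 0.2684 × 0.0563 + 0.3020 × 0.2031 = 0.3998.

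The same recursion gives the third column, with a further cumulative hold at 8 or more of 30.

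| True event rate | 10 only | 10 and 18 | 10, 18 and 30 |
|---|---|---|---|
| 10% | 7.0% | 8.0% | 8.2% |
| 20% | 32% | 40% | 44% |
| 25% | 47% | 59% | 66% |
| 30% | 62% | 75% | 83% |
| 33% | 70% | 83% | 90% |

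At the phase I rate for this schedule (1/13 = 7.7%), the hold probability goes from 3.6% with the current rule to 4.0% with both added looks.

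**Step 6: how firm are the phase I rates?** The exact 95% interval is 4% to 78% for 2/6 and 0.2% to 36% for 1/13. Neither fixes the rate closely.

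**The case against.** **Oversight does not end at patient 10.** A reader might infer that 30 patients are treated with no safety oversight. The documents do not support that. The DSMC reviews toxicity throughout, its list of materials is open-ended and includes laboratory values on request, and Appendix B allows a hold at any time. What is missing is a pre-specified numeric trigger. That part of the concern stands, because none of these provisions gives a threshold. The adverse events that section 12.2 names are unexpected ones, and section 7.4.4 exempts hematologic toxicity of any grade from expedited reporting to the Overall PI and the DFCI IRB.

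**The 33% is not this trial's expected rate.** A reader might also infer a 30% chance of missing a rate already known to apply. That is not supported either. The 2 of 6 comes from a schedule this trial does not use, was assessed at Day 42 rather than beyond day 45, and section 2.4.1 does not say whether those patients were free of leukemia. On the schedule used here the figure was 1 of 13, in line with the 10% planning rate. The trial's event also requires absence of disease. With the phase I response rate of 14/36 = 39% as a rough guide to clearance, 33% of all patients would mean about 86% of those who clear (0.333/0.389). That is a high bar, though leukemia-free aplastic patients may not have been counted as responders. In the other direction, other unacceptable toxicities also count toward the hold. The table therefore describes the total rate of countable events, whatever their mix.

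**The response look is not wholly blind to aplasia.** CR requires ANC above 1000, and CRi is not in the primary endpoint, so a marrow-clear patient with persistent neutropenia is not a response at the 18-patient look. This link is partial: CRp counts as a response, and the look acts only if total responses are 4 or fewer.

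**An early safety look followed by committee review is a legitimate choice after phase I.** It is. But section 13.1.1 says toxicity will be assessed within the two-stage design, and that design has no means of doing so.

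**Conclusion.** The point holds in this form: sections 13 and 13.1.1 do not fit together. Toxicity assessment is assigned to a design with response cut-offs only, and after the first 10 patients there is DSMC review but no numeric toxicity trigger. The existing rule is correctly calculated at 10%, but its chance of acting is 32% at a 20% event rate and 70% at 33%, and the plan discloses neither.

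The figures assume independent patients with a constant event rate, and each look taken once all its patients are assessable. Rates from 20% to 33% are scenarios for excess toxicity, not forecasts. The documents name no unacceptable rate, so they cannot show that any particular boundary is the right one. The gap between the two sections does not depend on which rate or boundary is chosen.

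**What to change.** Reconcile sections 13 and 13.1.1 (and the synopsis). Keep the 10-patient rule and add a cumulative toxicity hold, with the same event definition, at the existing 18-patient look, preferably with one later look. The sponsor should name its own unacceptable rate, choose the boundaries from it, report the overall hold probability at that rate as well as at 10%, and say whether accrual pauses until the patients at a look reach day 45. At 40 patients in 30 months (1.33 a month), about 2 would enrol during a 45-day wait.

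The boundaries of 5 of 18 and 8 of 30 are an illustration only. They have limits: at a 20% rate they still miss 56%, and at 33% about 7.5 points of the 20-point gain come from the look at 30, when only 10 patients remain. The 18-patient look alone captures most of the gain at 33% (70% to 83%).

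The cost is a short amendment using count-recovery data already collected. The look at 30 would be a new review. The false-hold chance at a 10% rate rises by about 1 percentage point, from 7.0% to between 8.0% and 8.2%, counting delayed recovery alone. A hold is a review, not a termination.
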